4.0 STUDY PLAN

4.1 Schema

4.2 Duration of Study

In this 5-year RCT, participants randomly assigned to the PERC group (the experimental group) will have access to the mHealth intervention titled Prostate Cancer Resources for Couples (PERC). The PERC users will have the chance to “meet” with a nurse educator via telephone and/or zoom video conferencing every 3-5 weeks for approximately 16-20 weeks. These will be scheduled via phone calls, emails or secure text messages (see section 4.3 below) to occur at these approximate time points: 1 week after completing the Baseline Survey (T1), and then three more at 3-5 week intervals for a total duration of 16 weeks. These intervals are flexible so that the patient/partner schedules can be accommodated and allow all 4 meetings to occur prior to the T2 survey. At the first intervention the Health Educator will describe how best to use the website and assist the couple to explore its features and different modules to manage post treatment symptoms whether emotional or physical. Participants will be encouraged to contact the Health Educator should they have questions.

Participants will also be given an option to utilize a tablet provided by the research team. If the participant does not have internet access, a Verizon jet pack (hot spot), along with user guide, will also be provided to the participant so that the surveys can be accessed. The tablet and jet pack will be returned when study participation is complete.

Content for subsequent interventions will be based on symptoms either member of the dyad is experiencing, making use of the PERC website for assistance in symptom

management. Dyads in the experimental group will have unlimited access to the PERC website after the final planned intervention.

Participants in the control group will have unlimited access to the NCI prostate cancer website. The Health Educator will have one phone meeting with them and their partners and answer any questions they have on accessing and navigating the NCI website. The control group will then receive emails and text messages approximately every 3-5 weeks until sixteen weeks to remind them to access the NCI website. As above, these intervals are flexible to allow for 3 reminders to be sent prior to the T2 Survey.

All participants will complete 3 follow-up surveys at around 4 (T2), 8 (T3), and 12 (T4) months post Baseline survey (T1)

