5.1 Time and Events Table

	Baseline (T1) PERC & Control	PERC Intervention	4, 8, and 12 months post- baseline (T2, T3, and T4) PERC & Control
Screening	X		
Informed Consent	X		
Randomization	X		
Quality of Life: Functional Assessment of Cancer Treatment (FACT-G): ^{176, 17*}	X	Phone and/or Zoom contact, with Questionnaires at time points	X
Personal factors: Demographics (age, race/ethnicity, income, and education)	X		
Charlson Comorbidity Index_Brief ^{177,178A}	X		X
PROMIS measures of pain, ¹⁷⁹ fatigue, ¹⁸⁰ sleep disturbance ^{181,182}	X		X
PROMIS Cancer Anxiety and Depression measures ^{182,185}	X		X

Couple factors: Relationship quality: Dyadic Adjustment Scale—Brief ^{186-188*}	X		X
Holmes and Rahe Scale	X		X
Cancer-related factors: Type of treatment [#]	X		X
Prostate cancer symptoms: Prostate cancer Index Composite (EPIC) ^{9,189**#}	X		X
Cancer care Financial Toxicity: COST-FACIT	x		x
Appraisal of illness: Appraisal of Illness scales ^{190,191*}	X		X
Coping Resources: Lewis Cancer Self-Efficacy Scale ¹⁹²	X		X
PROMIS Informational, Emotional, instrumental ¹⁹³⁻¹⁹⁵ and social Support ¹⁹⁶	X		X
Adapted Med Diet Screening and physical activity ^{201,202*}	X		X
Measure of Adult Sedentary Time (MOST)	X		X
eHealth Literacy Scale (eHEALS)	X		X
Modified RESIDE Physical Activity Screener	X		X
Perceived Ease of Use and Program Satisfaction ^{203,204*}			
Physical activity logs (health diary)	X		X
PERC web activity (automatic tracking)			X

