The research staff will ensure all entry criteria are met prior to the initiation of the protocol and all study procedures and reporting of adverse events and unanticipated events will be performed according to the IRB-approved protocol. Any actions taken and associated follow-up activities will be recorded in the study database. All intervention-related adverse events will be reported by the PIs to the IRB within 3-7 days. The PI will submit necessary reports to NINR. The PI and the Adverse Event Monitoring Committee will assess the level of risk from adverse events as mild (no interference in usual activities); moderate (some interference in usual activities); or severe (usual activities were significantly interrupted). The PI and the Adverse Event Monitoring Committee will rate the assessment of attribution to the study as not related, unlikely, possible, probable, or definite.

B.An Independent monitor, [name] (UNC Urologist), will be independent from the present study design and implementation and will be available as needed to advise oversight committees

To protect the confidentiality of participant data, the research team will conduct all research activities related to data processing involving identifiable data in a private office at the University of North Carolina-Chapel Hill School of Nursing (UNC-CH SON) that is dedicated to the project. This study has minimum hardcopy research records; the PI and the Safety Officer will ensure all records to be saved in a locked cabinet in the locked private office. With most data and documents being electronic, the PI and the Safety Officer will ensure that the identifiable and de-identified data and documents are saved separately in different project folders in the password-protected and encrypted, shared drive at the UNC-CH SON, which is on a secure UNC server. Only authorized key study personnel will have access to the identifiable information.

The de-identified electronic data will include survey recordings and the recordings of monthly meetings between the educator and study participants for

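### No step is specified for eliciting adverse events, and until about week 16 PERC couples have more live occasions than controls to volunteer one

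*Combined protocol and SAP*

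**What the plan says.** **Handling of events.** Section 7.4.2 sets out a three-level severity scale, a five-level attribution scale, a committee to apply both, and a window of 3 to 7 days for telling the IRB about intervention-related events. On procedure it says that "reporting of adverse events and unanticipated events will be performed according to the IRB-approved protocol". Sections 6.1 and 6.2 define unanticipated problems and say how they are reported.

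**Finding of events.** No section defines an adverse event for this trial, schedules a question about one, or gives a form or a collection window. Table 5.1 lists the instruments for T1 to T4, with rows such as "PROMIS Cancer Anxiety and Depression measures", and none of the rows is for adverse events.

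**Contact in the PERC arm.** Section 4.2 schedules educator meetings at "1 week after completing the Baseline Survey (T1), and then three more at 3-5 week intervals for a total duration of 16 weeks", with intervals kept flexible to "allow all 4 meetings to occur prior to the T2 survey". On the later meetings it says: "Content for subsequent interventions will be based on symptoms either member of the dyad is experiencing". Couples are also encouraged to contact the educator with questions, and section 1.3 gives them a moderated online forum.

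**Contact in the control arm.** Section 4.2 says: "The Health Educator will have one phone meeting with them and their partners". Emails and texts follow, and "these intervals are flexible to allow for 3 reminders to be sent prior to the T2 Survey".

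**Contact in both arms.** Every participant has follow-up surveys at about 4, 8 and 12 months. Under section 4.3 these are telephone interviews by staff blinded to assignment.

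**The concern.** The safety plan has rules for judging events but no stated source of events to judge. The procedural sentence in section 7.4.2 points to the protocol, and the protocol contains no such procedure.

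Without a scheduled question, the record depends on who happens to mention what, and to whom. That opportunity is not the same in the two arms during the intervention period. PERC couples speak with an educator four times, and the later conversations are built around current symptoms, which is where a new problem is likely to be mentioned. Controls speak with the educator once and then receive written reminders.

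Two uses of the record are at stake. Sections 4.4 and 6.1 state that risk is minimal, and an incomplete spontaneous record is weak support for that. And if event counts are ever set out by arm, a true difference could not be separated from a difference in contact. A question that was not asked during follow-up cannot be added at the analysis stage.

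**Working it through.** **1. Count of educator meetings (section 4.2).** PERC: 1 + 3 = 4, which matches the stated total of four before T2. Control: 1. With the first PERC meeting at week 1 and three intervals of 3 to 5 weeks, the last falls between week 1 + 3×3 = 10 and week 1 + 3×5 = 16.

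**2. Count of all scheduled live contacts after randomization.** Add the three shared telephone surveys: PERC 4 + 3 = 7, control 1 + 3 = 4, ratio 7/4 = 1.75. Emails and texts are not counted. Forum posts and unscheduled calls to the educator are left out because the documents give no numbers for them.

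**3. What that could do to recorded events.** The documents give no chance of volunteering an event, so it is an assumption here. Let p be the probability that a persisting event is mentioned at any one live contact, with contacts independent and all attended. The chance of capture over k contacts is 1 − (1 − p)^k. For an event present before the first meeting, k = 7 under PERC and k = 4 under control:

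| p (assumed) | PERC, 1 − (1 − p)^7 | Control, 1 − (1 − p)^4 | Ratio |
|---|---|---|---|
| 0.1 | 0.522 | 0.344 | 1.52 |
| 0.2 | 0.790 | 0.590 | 1.34 |
| 0.3 | 0.918 | 0.760 | 1.21 |
| 0.5 | 0.992 | 0.938 | 1.06 |

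**4. Dependence on time of onset.** The ratio is not constant. If the control meeting falls at about the same time as the first PERC meeting (its date is not given), an event starting just after both has 6 contacts left against 3. At p = 0.1 that gives (1 − 0.9^6)/(1 − 0.9^3) = 0.469/0.271 = 1.73. At p = 0.5 it gives 0.984/0.875 = 1.13. An event starting after the last PERC meeting but before T2 has 3 contacts against 3, and one starting after T2 has 2 against 2. The ratio for scheduled contacts is then 1.0, and only the forum and unscheduled educator contact still differ. The imbalance therefore belongs to roughly the first 16 weeks.

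**5. After the fix.** With an identical question at T2, T3 and T4, solicited contacts are 3 in each arm. Suppose each solicited call captures an event with probability q, and each educator meeting still yields a volunteered mention with probability 0.2 (both assumed). Capture is 1 − (1 − q)^3 × 0.8^4 under PERC and 1 − (1 − q)^3 × 0.8 under control. At q = 0.6: 0.974 against 0.949, ratio 1.03. At q = 0.9: 0.9996 against 0.9992, ratio 1.00. Restricting the comparison to solicited events makes capture equal in the two arms under the same q.

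**The case against.** The strongest reply is that this is a low-risk behavioural trial whose plausible harms are already measured. Table 5.1 schedules pain, fatigue, sleep, anxiety, depression, prostate symptoms (EPIC) and relationship quality (Dyadic Adjustment Scale) at T2 to T4 in both arms, and blinded staff collect them. For a website with educator calls, worse distress or a strained relationship is what one would look for. This largely stands: those scores give a partial and even-handed view of harm. But section 7.3 plans no harms analysis of them, no threshold triggers a review, and none of them asks whether something untoward has happened.

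Second, section 7.3 plans no comparison of adverse events by arm, and adverse events are not an endpoint, so no planned estimate is biased. That stands in full, and it limits the weight of the point.

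Third, oversight exists: section 7.4.2 reports that a DSMB was consulted and judged unnecessary, and names a monitoring committee, an independent monitor and a safety officer. That answers who reviews events, but not how events reach them.

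Fourth, asking blinded interviewers about adverse events may lead participants to mention the website or the educator, and so unblind the staff who collect the self-reported primary outcome. This is a real cost, and it shapes the fix.

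A reader might infer that participants are never asked about adverse events. The documents do not show that. They include no survey scripts, so they support only the statement that no such question is specified.

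**Conclusion.** The point holds as a gap in ascertainment. The protocol specifies how adverse events are judged and reported but no step that elicits them, and until about week 16 PERC couples have more scheduled live occasions to volunteer one: 7 against 4 over the whole trial, with the entire difference arising before T2. For a persisting event present from the start, PERC would be expected to record about 1.5 times (p = 0.1) to 1.06 times (p = 0.5) as many events at equal true rates. These ratios rest on an assumed p, on independent and fully attended contacts, and on p being the same for educator meetings and surveys. They illustrate the possible size and do not estimate an actual bias.

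Three stronger readings are not supported:

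- **A two- to three-fold excess under PERC.** Counting educator meetings alone (4 against 1) gives ratios of 3.4 at p = 0.1 and 1.9 at p = 0.5, but this leaves out three live interviews, common to both arms, at which an event can also be mentioned.
- **Certainty that PERC will show more events.** The documents do not establish the direction or size of any actual bias.
- **Events in months 4 to 12 largely missed, with minimal risk impossible to check.** Scheduled contact is equal after the last meeting, and the shared T2 to T4 scores cover part of the plausible harm.

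The efficacy analysis is unaffected. What is weakened is the use of the adverse-event record to support the minimal-risk statement or to compare arms. The change is worth making before further follow-up calls take place.

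**What to change.** - State in section 7.4.2 what counts as an adverse event and how it is collected.
- Add one short, identically worded adverse-event question to the T2, T3 and T4 telephone surveys, for patients and partners in both arms. Place it after the QOL and all other outcome items, and word it so that it does not prompt mention of the website or the educator.
- Add the matching row to Table 5.1.
- State in section 7.3 that any by-arm summary uses only these solicited events. List events volunteered to the educator or on the forum separately.

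**Cost.** A protocol amendment, a few REDCap fields, slightly longer calls, and more events to log, most of them probably unrelated to the trial. There are no new visits or staff. A small risk of unblinding the interviewer remains. Asking the question last protects the outcome data of that call, though not those of a later call by the same interviewer.

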8.0 STUDY MANAGEMENT

8.1 Institutional Review Board (IRB) Approval and Consent

It is expected that the IRB will have the proper representation and function in accordance with federally mandated regulations. The IRB should approve the consent form and protocol.

In obtaining and documenting informed consent, the investigator should comply with the applicable regulatory requirement(s), and should adhere to Good Clinical Practice (GCP) and to ethical principles that have their origin in the Declaration of Helsinki.

Before recruitment and enrollment onto this study, we will mail study brochure and consent information to potential participants referred by the NC Central Cancer Registry. The patient and his partner will also be given a full explanation of the study and will be given the opportunity to review the study information and the consent form via telephone. Each consent form will include all the relevant elements currently required by the UNC IRB or state regulations. Once this essential information has been provided to the patient and his partner the investigator is assured that they understand the implications of participating in the study, they will be asked to give consent to participate in the study by consenting verbally the IRB-approved consent form when potential participants interviewed and screened via telephone. All consent processes will be recorded and saved in a file separate from other deidentified study materials in password protected, encrypted shared drive on the UNC server.

8.2 Required Documentation

Before the study can be initiated at any site, the following documentation must be provided to the Clinical Protocol Office (CPO) at the University of North Carolina.

- A copy of the official IRB approval letter for the protocol and informed consent
- CVs and medical licensure for the principal investigator and any associate investigators who will be involved in the study
- A copy of the IRB-approved consent form

8.3 Registration Procedures

REDCap will be used to keep track of participants' recruitment and other project activities. We have used REDCap to manage our patient recruitment and project activities in the past. We will register all enrolled participants in OnCore. We have also registered this project on CT.gov.

8.4 Adherence to the Protocol

Except for an emergency situation in which proper care for the protection, safety, and well-being of the study patient requires alternative treatment, the study shall be conducted exactly as described in the approved protocol.

8.4.1 Emergency Modifications

UNC investigators may implement a deviation from, or a change of, the protocol to eliminate an immediate hazard(s) to trial subjects without prior UNC IRB approval.

8.4.2 Single Patient/Subject Exceptions

Any request to enroll a single subject who does not meet all the eligibility criteria of this study requires the approval of the UNC Principal Investigator and the UNC IRB.

No

8.4.3 Other Protocol Deviations/Violations

According to UNC's IRB, a protocol deviation is any unplanned variance from an IRB approved protocol that:

- Is generally noted or recognized after it occurs
- Has no substantive effect on the risks to research participants
- Has no substantive effect on the scientific integrity of the research plan or the value of the data collected
- Did not result from willful or knowing misconduct on the part of the investigator(s).

An unplanned protocol variance is considered a violation if the variance meets any of the following criteria:

- Has harmed or increased the risk of harm to one or more research participants.
- Has damaged the scientific integrity of the data collected for the study.
- Results from willful or knowing misconduct on the part of the investigator(s).
- Demonstrates serious or continuing noncompliance with federal regulations, State laws, or University policies.

If a deviation or violation occurs please follow the guidelines below:

Protocol Deviations: UNC personnel will record the deviation in OnCore® (or other appropriate database set up for the study), and report to any sponsor or data and safety monitoring committee in accordance with their policies. Deviations should be summarized and reported to the IRB at the time of continuing review.

Protocol Violations: Violations should be reported by UNC personnel within one (1) week of the investigator becoming aware of the event using the same IRB online mechanism used to report UPIRSO.

Unanticipated Problems Involving Risks to Subjects or Others (UPIRSO):

Any events that meet the criteria for “Unanticipated Problems” as defined by UNC’s IRB (see section 6.1) must be reported by the Study Coordinator using the IRB’s web-based reporting system.

8.5 Amendments to the Protocol

Should amendments to the protocol be required, the amendments will be originated and documented by the Principal Investigator at UNC. It should also be noted that when an amendment to the protocol substantially alters the study design or the potential risk to the patient, a revised consent form might be required.

The written amendment, and if required the amended consent form, must be sent to UNC’s IRB for approval prior to implementation.

8.6 Record Retention

Study documentation includes all Case Report Forms, data correction forms or queries, source documents, Sponsor-Investigator correspondence, monitoring logs/letters, and regulatory documents (e.g., protocol and amendments, IRB correspondence and approval, signed patient consent forms).

Source documents include all recordings of observations or notations of clinical activities and all reports and records necessary for the evaluation and reconstruction of the clinical research study.

Government agency regulations and directives require that all study documentation pertaining to the conduct of a clinical trial must be retained by the study investigator. In the case of a study with a drug seeking regulatory approval and marketing, these documents shall be retained for at least two years after the last approval of marketing application in an International Conference on Harmonization (ICH) region. In all other cases, study documents should be kept on file until three years after the completion and final study report of this investigational study.

8.7 Obligations of Investigators

The Principal Investigator is responsible for the conduct of the clinical trial at the site in accordance with Title 21 of the Code of Federal Regulations and/or the Declaration of Helsinki. The Principal Investigator is responsible for personally overseeing the treatment of all study patients. The Principal Investigator must assure that all study site personnel, including sub-investigators and other study staff members, adhere to the study protocol and all FDA/GCP/NCI regulations and guidelines regarding clinical trials both during and after study completion.

The Principal Investigator at each institution or site will be responsible for assuring that all the required data will be collected and entered onto the Case Report Forms. Periodically, monitoring visits will be conducted and the Principal Investigator will provide access to his/her original records to permit verification of proper entry of data. At the completion of the study, all case report forms will be reviewed by the Principal Investigator and will require his/her final signature to verify the accuracy of the data.

